# Inverse Probability Weighting (IPW; Secondary Objectives)

Do not distribute for purposes outside of specific activities related to development of FDAMAs114 compliant pieces. Content within this protocol is subject to change based on communication planning and input by external review committees.

Pfizer Confidential

Page 28 of 37

Apixaban NON-INTERVENTIONAL STUDY PROTOCOL

IPW uses propensity scores to obtain estimates of the average treatment and censoring effect. Propensity scores will be calculated using repeated measures logistic models with: 1) ever-treated with OAC and never-treated with OAC cohorts; 2) each DOAC treated and never-treated with OAC cohorts included in the model, using never-treated patients as the reference (i.e. control cohort). Appropriate correlation structure will be chosen based on the data and clinical rationale.

The propensity score is defined as the probability of a patient receiving OAC/DOAC treatment or being censored conditional on both time-dependent covariates (e.g., comorbidities) and time-independent baseline covariates (age, gender, race, and baseline value for each of the time-dependent variables). The list of variables included in the logistic model will be based on clinical rationale. The propensity score acts as a balancing score among the cohorts.

After calculating the propensity score, the distribution of the propensity scores will be reviewed.

Each patient's weight is equal to the inverse of the probability of their treatment option and censoring (weight=1/propensity score). The numerator of the weight is the propensity score that a patient is on observed treatment/censored in a time period conditional on the baseline covariates. Denominator of the weight is the same propensity score conditional on time-dependent (factors such as CHA2DS2-VASc score, history of bleeding, etc.) and time-independent confounders. If an ever-treated patient has a very low propensity score, a very large weight can be created. Large weights can increase the variability of estimated treatment effect. In order to address this, the weights will be stabilized. Stabilized weights for treatment and censoring will be calculated for each time period of a patient. This reduces the variability of the weights.

$$SW = \prod_{k=0}^{t} \frac{f[A(k) | \overline{A}(k-1), V]}{f[A(k) | \overline{A}(k-1), \overline{L}(k)]}$$

The distribution of the stabilized weight will be reviewed. If no extreme outliers are observed, the stabilized weights will be applied to the sample. In cases of extreme outliers, the large weights could be set to a less extreme value (e.g. recoding all weights that are outside 5th and 95th percentile to the 5th and 95th value, respectively). If needed, truncation can be done after stabilizing the weights.

Pfizer Confidential

Page 29 of 37

Do not distribute for purposes outside of specific activities related to development of FDAMAs114 compliant pieces. Content within this protocol is subject to change based on communication planning and input by external review committees.

Apixaban NON-INTERVENTIONAL STUDY PROTOCOL

After the weights are applied, the balance of the time-dependent and time-independent covariates will be assessed.

First, the means and proportions of baseline variables will be compared. The standardized difference compares the difference in means in units of the standard deviation. If the standardized difference is less than 10%, the covariates will be considered balanced.

For continuous variables, the balance of the distribution will also be assessed. The high-order movements and interactions between variables should be similar between cohorts. The standardized difference will be used to compare the mean of the square of continuous variables. Graphical comparisons of the distribution of continuous variables will be completed. Side-by-side boxplots and empirical cumulative distribution functions will be used to the compare the distribution of continuous covariates in the unweighted and weighted samples. Since the graphical approach can be subjective, a numerical method for comparing the distribution of continuous baseline covariates will also be completed. Kolmogorov-Smirnov test allows a comparison of the distribution of a continuous variable between two independent groups.33.34.35.36

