#### Apixaban NON-INTERVENTIONAL STUDY PROTOCOL

- 4. Compare the risk of death among elderly patients treated versus untreated with OACs in the Medicare NVAF population.
- 5. Compare the all-cause health care costs among elderly patients treated versus untreated with OACs in the Medicare NVAF population.

**Study Design:** The study will be a longitudinal retrospective cohort analysis using the US Centers for Medicare & Medicaid Services (CMS) Medicare dataset from 01JAN2012-31DEC2016. The study will designate a 12-month baseline period prior to the identification period (01JAN2013-31DEC2016). This database only includes patients enrolled in fee-for-service (FFS) Medicare; those enrolled in managed-care plans will be excluded. Further, patient eligibility will be based on selection from the database according to the following inclusion and exclusion criteria (sections 2).

**Population:** Elderly patients (aged  $\geq 65$  years) will be required to have  $\geq 1$  inpatient or  $\geq 2$  outpatient medical claims (the 2 outpatient claims are  $\geq 7$  days apart) for AF during the identification period for the primary and secondary objectives. For the primary objective, two mutually-exclusive NVAF patient cohorts will be created: ever-treated with OAC and never-treated with OAC. For the secondary objective assessing clinical and healthcare utilization and costs, treatment status will be a time-varying covariate and ever-treated patients will contribute time-not-on-treatment to untreated effect.

For the primary and secondary objectives, the ever-treated with OAC population cohort will include newly diagnosed NVAF patients who ever initiated oral anticoagulant (OAC) treatment (apixaban, dabigatran, edoxaban, rivaroxaban, and warfarin) during the study period identified from 01JAN2013-31DEC2016. The never-treated with OAC population cohort will include newly diagnosed NVAF patients without any OAC claim from 01JAN2013-31DEC2016.

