For the primary and secondary objectives, the first AF diagnosis date during the identification period will be used as the index date for both ever-treated and never-treated cohorts. Across both ever-treated and never-treated cohorts, all patients will be required to have a  $CHA_2DS_2$ -VASc $\geq 2$  and 12-months of continuous health plan enrollment, with medical and pharmacy benefits before the index date (baseline period). For the primary objective and high-risk subgroup analyses, patients will also be required to have 6-month continuous health plan enrollment, with medical and pharmacy benefits after the index date.

For the primary objective and high-risk subgroup analyses, the following patients will be excluded: an AF diagnosis any time prior to the first AF diagnosis; medical claims indicating a diagnosis or procedure for mitral valvular heart disease or heart valve replacement/transplant;

Do not distribute for purposes outside of specific activities related to development of FDAMAs114 compliant pieces. Content within this protocol is subject to change based on communication planning and input by external review committees.

Apixaban NON-INTERVENTIONAL STUDY PROTOCOL

or use of OACs during the baseline period. For the secondary objective assessing effectiveness, safety, and cost outcomes, patients will be further excluded if they had any of the following: venous thromboembolism; transient AF during the baseline period; pregnancy during the study period; hip/knee replacement surgery within 6 weeks pre-index date; or follow-up period = 0 day. In addition, among patients ever treated with an OAC, those with >1 OAC prescription claim at the index date will be excluded as well.

**Variables:** Baseline demographic and clinical characteristics will include age, gender, race, geographic region, Medicaid dual eligibility, Part-D low income subsidy, Charlson comorbidity index (CCI), CHADS2, CHA2DS2-VASc, HAS-BLED scores, prior bleeding/stroke events, congestive heart failure, diabetes, hypertension, chronic obstructive pulmonary disease, renal disease, myocardial infarction, dyspepsia or stomach discomfort, peripheral arterial disease, transient ischemic attack, coronary artery disease, history of falls, medication use, and index dose of DOAC. Baseline all-cause health care costs and utilization will be included.

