# 7. Research Question and Objectives

Primary Objective

- 1. Estimate patients ever-treated and never-treated with OACs and the predictors of OAC treatment among elderly Medicare NVAF patients. The following comparative cohorts will be included:
  - Ever-treated versus never-treated with OACs
  - Treated with DOACs versus never-treated with OACs
  - Treated with warfarin versus never-treated with OACs
  - Treated with DOACs versus treated with warfarin

Secondary Objectives

- 1. Analyze high-risk patient subgroups, including CHA2DS2-VASc score and age subgroups, for the primary objective. The same comparative cohorts as the primary objective will be included. The following subgroups will be examined:
  - ♦ CHA2DS2-VASc score subgroups: 2-3, 4-5, and  $\geq 6$
  - Age subgroups: 65-74, 75-79, and  $\geq$ 80 years
- 2. Compare the risk of major bleeding and major bleeding-related costs among elderly patients treated versus untreated with OACs in the Medicare NVAF population. The following comparative cohorts will be included:
  - Treated versus untreated with OACs
  - ✤ Apixaban versus untreated with OACs
  - Dabigatran versus untreated with OACs
  - Rivaroxaban versus untreated with OACs
  - Warfarin versus untreated with OACs
- 3. Compare the risk of stroke/SE and stroke/SE-related costs among elderly patients treated versus untreated with OACs in the Medicare NVAF population. The same

Do not distribute for purposes outside of specific activities related to development of FDAMAs114 compliant pieces. Content within this protocol is subject to change based on communication planning and input by external review committees.

Apixaban NON-INTERVENTIONAL STUDY PROTOCOL

comparative cohorts as secondary objective 2 will be included.

- 4. Compare the risk of death among elderly patients treated versus untreated with OACs in the Medicare NVAF population. The same comparative cohorts as secondary objective 2 will be included.
- 5. Compare the all-cause health care costs among elderly patients treated versus untreated with OACs in the Medicare NVAF population. The same comparative cohorts as secondary objective 2 will be included.

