# 8.2.3. Cohorts

Patients eligible according to the above criteria will be assigned to the following cohorts:

Do not distribute for purposes outside of specific activities related to development of FDAMAs114 compliant pieces. Content within this protocol is subject to change based on communication planning and input by external review committees.

Apixaban NON-INTERVENTIONAL STUDY PROTOCOL

- 1) Ever-Treated Cohort: NVAF Patients had ≥1 pharmacy claim for apixaban, dabigatran, edoxaban, rivaroxaban, or warfarin from 01JAN2013-31DEC2016 on or after the first AF diagnosis
  - a. Apixaban cohort: Patients who initiated with apixaban on or after index date
  - b. Dabigatran cohort: Patients who initiated with dabigatran on or after index date
  - c. **Edoxaban cohort:** Patients who initiated with edoxaban on or after index date. Given the small sample size, edoxaban patients will not be included in the secondary clinical and healthcare utilization and costs analyses.
  - d. Rivaroxaban cohort: Patients who initiated with rivaroxaban on or after index date
  - e. Warfarin cohort: Patients who initiated with warfarin on or after index date
- 2) Never-Treated Cohort: NVAF patients with no pharmacy claim for an OAC from 01JAN2013-31DEC2016

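### The drug-specific weights use a reference group defined by future OAC claims, which drops death-free untreated time and biases the drug-versus-untreated death comparisons towards the drug

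*Protocol*

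**What the plan says.** - Time zero is the first AF diagnosis, which "will be used as the index date for both ever-treated and never-treated cohorts" (Protocol Section 3).
- A drug cohort may start treatment well after time zero, for example "Patients who initiated with apixaban on or after index date" (Section 8.2.3).
- The never-treated cohort is "NVAF patients with no pharmacy claim for an OAC from" the start of 2013 to the end of 2016 (Section 8.2.3). Membership is known only when follow-up is complete.
- Section 8.7, Inverse Probability Weighting, names two sets for the weight models. Item 1, the overall comparison, uses "ever-treated with OAC and never-treated with OAC cohorts". Item 2, the drug-specific comparisons, uses "each DOAC treated and never-treated with OAC cohorts included in the model, using never-treated patients as the reference".
- Section 3 says that "ever-treated patients will contribute time-not-on-treatment to untreated effect". The Cox section of 8.7 makes treatment time-varying for the same purpose and applies the IPW weights.
- Sections 3 and 7 list the comparisons as pairs: treated, apixaban, dabigatran, rivaroxaban and warfarin, each against untreated. The last is "Warfarin versus untreated with OACs".

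**The concern.** Consider the apixaban comparison read as a pair. A patient who is untreated for eight months and then starts warfarin is neither an apixaban initiator nor never-treated. That patient gets no weight, and the eight untreated months drop out. The patient had to be alive to fill the warfarin prescription, so those months contain no death. Removing them leaves the untreated deaths unchanged and shrinks the untreated person-time, which raises the untreated death rate.

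Weighting on measured history cannot repair this, because membership depends on the future. Item 1 excludes no starters, so the overall and drug-specific analyses would also use different reference groups. Death is secondary objective 4, compared for four drugs, and a spurious mortality benefit of this kind could be taken for a real one.

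**Working it through.** The protocol gives no figure to reproduce here. The direction follows from an identity; the size needs assumed inputs.

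**Identity for death under a true null.** Let λ be the common death rate, P all untreated person-time, and P_o the untreated time of patients who later start an OAC that is not in the model. Untreated deaths are λP, and none fall in P_o.
- All untreated time kept: ratio = λ / (λP/P) = 1.
- P_o dropped: ratio = λ / [λP/(P − P_o)] = 1 − P_o/P.

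The ratio is below 1 whenever any such time is dropped. The studied drug's own pre-treatment time stays in P, so the loss is partial.

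**Base case.** From the protocol: a four-year identification window ending with the data. Assumed: entry uniform over that window, death 0.15/yr, 60% of patients potential starters, 30% of those starting at index and the rest at 0.6/yr, and the studied drug taking 25% of starts.
- Mean time to an event at rate h or end of data: A(h) = 1/h − (1 − e^(−4h))/(4h²). A(0.15) = 6.667 − 5.013 = 1.653; A(0.75) = 1.333 − 0.422 = 0.911.
- Late potential starters: 0.60 × 0.70 = 0.42 of patients.
- P = 0.40 × 1.653 + 0.42 × 0.911 = 1.044 years per patient.
- Untreated time that ends in any OAC start: 0.42 × 0.6 × ∫₀⁴ t(1 − t/4)e^(−0.75t)dt = 0.42 × 0.6 × 0.740 = 0.187.
- Fraction: 0.187/1.044 = 0.179.
- Pairwise, 75% of this is lost: 1 − 0.75 × 0.179 = **0.87**.

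A simulation with the same inputs gave a rate ratio of 0.86 and a Cox HR of 0.87 (SE 0.03 on the log scale). With all untreated time kept it gave 0.99 and 1.00.

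**Varying the assumptions (pairwise reading).**

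| Change from base | Identity | Simulated rate ratio |
|---|---|---|
| Drug share 10% | 1 − 0.90 × 0.179 = 0.84 | 0.83 |
| Drug share 40% | 1 − 0.60 × 0.179 = 0.89 | 0.88 |
| Late starts 0.2/yr | 1 − 0.75 × 0.096 = 0.93 | 0.96 |
| Late starts 1.5/yr, 70% potential starters, 40% of them at index | 1 − 0.75 × 0.227 = 0.83 | 0.82 |
| Death 0.08/yr | 1 − 0.75 × 0.183 = 0.86 | 0.85 |

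The 0.96 includes simulation noise: the full comparison in that run read 1.03, and 0.96/1.03 = 0.93.

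A separate monthly model assumed death at 1-2%/month and entry over 48 months. It gave these Cox HRs, and 1.00 whenever the full risk set was kept:
- OAC start 10%/month for 3 months, then 2%: 0.84-0.85 for a drug with 30% of starts, 0.80-0.81 for one with 10%.
- 25%/month for 2 months, then 1%: 0.88-0.91.
- Constant 3%/month, an extreme case: 0.74-0.81.

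**Multi-category reading.** If one model holds all DOAC cohorts, mainly warfarin starters are lost. Assume that they are 30-50% of starts. Base case: 1 − 0.30 × 0.179 = 0.95 to 1 − 0.50 × 0.179 = 0.91. With late starts at 0.2/yr and 30% lost: 1 − 0.30 × 0.096 = 0.97. The monthly scenarios give about 0.85-0.96.

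**Stroke/SE.** Dropped time can contain a stroke, so the identity does not apply. Simulated null ratios, all untreated time kept → pairwise set:
- Starts independent of stroke: 1.05 → 1.05, no shift.
- A stroke doubles the start rate: 1.01 → 1.07.
- A stroke triples the start rate and doubles mortality: 0.99 → 1.06.
- A stroke triples mortality without prompting a start: 1.01 → 0.98.

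The sign depends on whether events prompt treatment. The same logic applies to bleeding.

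**The case against.** The best defence is that the intended rule is already in the protocol. Section 3 and the Cox section of 8.7 both count ever-treated patients' untreated time, ever-treated covers any OAC, and nothing explicitly limits the Cox risk set to never-treated patients. Item 2 can also be read as one model with all DOAC cohorts in it. The objectives concerned are secondary and, under Section 8.7, optional.

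Much of this is fair. It shows that the statements conflict, but not that item 2 is harmless. The Cox model takes its weights from item 2, and a patient outside both cohorts has none. Nothing says that starters of another OAC stay in as untreated until that start. The multi-category reading shrinks the loss without removing it, because warfarin is not a DOAC.

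Several stronger readings are tempting but not supported:
- A reader might infer that the stroke/SE and bleeding hazard ratios also favour the drug. They need not; the shift can run the other way.
- A reader might infer that drugs with few initiators are always worse affected and so are distorted against each other. That depends on the pairwise reading. With one DOAC model the size hardly varies with the drug's share (0.934 against 0.932 at 10% and 30%), and Section 7 plans no outcome contrast between drugs.
- A reader might infer that leaving out edoxaban starters ("edoxaban patients will not be included in the secondary clinical and healthcare utilization and costs analyses") matters materially. It is the same kind of selection, but at an assumed 1% of starts it gives 1 − 0.01 × 0.179 = 0.998.
- A reader might infer that warfarin has no weights at all. The Cox section plans weighting for each OAC; the fault is that item 2 names only DOACs.

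**Conclusion.** Item 2 of the weighting section is wrong as written for the drug-specific death comparisons. It conditions the reference on future treatment, contradicts the protocol's own rule on untreated time, and pushes a null death ratio below 1 on either reading. The size is roughly 0.82-0.96 read pairwise, which is the natural reading beside the listed pairs, with about 0.74 at the extreme. It is roughly 0.85-0.97 for a single DOAC model. The direction for death rests only on later starters having to survive to their start. The size rests on assumed death rates, start rates and drug shares, none of which the protocol gives. For stroke/SE and major bleeding, bias is possible but its direction is not fixed. The overall treated-versus-untreated model does not share the defect. The warfarin gap in item 2 is a separate wording mismatch to close in the same edit.

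**What to change.** Rewrite item 2 of the weighting section in Protocol 8.7, replacing the clause that makes never-treated patients the reference or control cohort. For each OAC compared (apixaban, dabigatran, rivaroxaban and warfarin):

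1. Fit the treatment-weight model and the Cox model on all eligible patients from the index date.
2. Make untreated person-time the reference, whatever the patient receives later.
3. Count a patient as exposed from first fill of the studied drug.
4. Censor an untreated patient at first fill of any other OAC, edoxaban included, and handle that censoring with the censoring weights already planned.

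This removes the selection on either reading of the current sentence and brings the weighting section into line with Section 3 and the Cox section. The cost models use the same weights, so the wording should carry through to them.

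The cost is wording and programming on the same data. The price is greater reliance on the censoring-weight model: starting another OAC becomes a censoring event, so that model must capture what leads to it.

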# 8.2. Setting

Ever treated with OAC and never treated with OAC patients will be selected from 01JAN2013-31DEC2016. To ensure access to the patients' complete medical history, they will be required to have continuous health plan enrollment for the 12 months before the first AF diagnosis date/index date (baseline period). Patient data will be assessed from index date until the earliest of death, health plan disenrollment, treatment switch (treated patients), discontinuation (treated patients), or 31DEC2016 (end of study).

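### The censoring weight is mis-specified: the text inverts the probability of being censored, and the printed formula has no censoring term

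*Protocol*

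**What the plan says.** All references are to the Protocol. The Inverse Probability Weighting text in Section 8.7 makes five statements about the weight:

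- Score: "The propensity score is defined as the probability of a patient receiving OAC/DOAC treatment or being censored conditional on both time-dependent covariates".
- Weight: "Each patient's weight is equal to the inverse of the probability of their treatment option and censoring (weight=1/propensity score".
- Numerator: "The numerator of the weight is the propensity score that a patient is on observed treatment/censored in a time period", given baseline covariates.
- Denominator: "Denominator of the weight is the same propensity score conditional on time-dependent" and time-independent confounders.
- Promise: "Stabilized weights for treatment and censoring will be calculated for each time period of a patient".

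The one formula printed below these statements is a product over periods k. Its numerator is the density of treatment A(k) given treatment history and V. Its denominator is the density of A(k) given treatment history and covariate history L(k). It has no censoring indicator and does not condition on being uncensored.

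Section 8.2 ends follow-up at the earliest of death, disenrollment, "treatment switch (treated patients), discontinuation (treated patients), or 31DEC2016 (end of study". The Section 8.7 text on the time-varying Cox models and on the marginal structural models for cost applies these weights to the analyses of objectives 2-5.

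**The concern.** An inverse-probability-of-censoring weight lets the patients who remain stand in for similar patients who have left. It therefore has to use the probability of remaining. The protocol names the opposite event, joins it with receipt of treatment in a single probability although the two are separate processes, and then prints a formula from which censoring is absent.

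The weight has real work to do here. Switching and discontinuation end follow-up in treated patients only, and stopping an anticoagulant may plausibly be related to prognosis. Under that rule the censoring weight is the only stated adjustment for informative stopping. The sensitivity analyses in Section 8.8 do not replace it: a shorter allowable gap produces more discontinuation, the competing-risk analysis addresses death only, and censoring at 6 months leaves earlier stopping as it was.

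The protocol has chosen to define the weight, so this is a rule stated wrongly and not a detail left for a later document.

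**Working it through.** The protocol gives no figure to reproduce. The check compares the weight that is needed with the weights that are written.

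**1. Weight needed.** Let C(k)=0 mean still uncensored at period k. A retained period needs the factor P[C(k)=0 | V] / P[C(k)=0 | L], both given treatment history and C(k-1)=0.

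**2. Definition taken literally.** The censoring part becomes P[C(k)=1 | V] / P[C(k)=1 | L]. As an assumed example, take a patient whose censoring risk per period is 10%, where baseline covariates alone give 4%:

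- needed: 0.96/0.90 = 1.067, and over six periods 1.067^6 = 1.47
- literal: 0.04/0.10 = 0.40, and over six periods 0.40^6 = 0.004

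The patient who should count for more counts for less.

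**3. Formula taken literally.** It contains only A(k), so the censoring factor is 1 for everyone.

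**4. Illustration of size.** All of the set-up is assumed. One binary risk factor L has prevalence 50%. Outcome risk is r0 = 1.6% without it and r1 = 3.7% with it; these borrow the two annual stroke/SE rates in Section 8.5 as low and high values. Overall censoring is 10%, 30% or 53.7%; these figures come from the loss-of-follow-up column of Table 4, which does not say that they measure stopping or switching. Censoring is more likely when L=1, with odds ratio (OR) 1.5, 2 or 3.

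With prevalence p_L, censoring probability c_L and weight w_L, the weighted risk among the uncensored is

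sum[p_L (1-c_L) w_L r_L] / sum[p_L (1-c_L) w_L].

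The true risk is (1.6 + 3.7)/2 = 2.650%. Under the literal weight, w_L is proportional to 1/c_L, so the expression reduces to (OR x r0 + r1)/(OR + 1) whatever the overall censoring. For OR 3 this is (4.8 + 3.7)/4 = 2.125%.

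| OR | Censored | No censoring factor (formula) | Literal definition | P[C=0] weight |
|---|---|---|---|---|
| 1.5 | 10% | 2.629% (-0.8%) | 2.440% (-7.9%) | 2.650% |
| 1.5 | 53.7% | 2.536% (-4.3%) | 2.440% (-7.9%) | 2.650% |
| 2 | 30% | 2.542% (-4.1%) | 2.300% (-13.2%) | 2.650% |
| 3 | 10% | 2.596% (-2.0%) | 2.125% (-19.8%) | 2.650% |
| 3 | 53.7% | 2.348% (-11.4%) | 2.125% (-19.8%) | 2.650% |

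In the last row c0 = 0.404 and c1 = 0.670. The needed weights are 0.463/0.596 = 0.78 for L=0 and 0.463/0.330 = 1.40 for L=1. The literal ones are 0.537/0.404 = 1.33 and 0.537/0.670 = 0.80.

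**5. Direction.** If high-risk patients are instead less likely to be censored (OR 1/3, 53.7% censored), the symmetry of the set-up reverses the signs. With no factor the risk is 5.300 - 2.348 = 2.952% (+11.4%), and with the literal weight 5.300 - 2.125 = 3.175% (+19.8%). The sign of the bias therefore depends on who stops.

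**6. Is stopping censoring at all?** Section 8.2 says that it is. The Population paragraph of the Abstract assigns off-treatment time of ever-treated patients to the untreated effect, and the Cox text in Section 8.7 makes treatment time-varying. Neither says whether this includes time after discontinuation. If it does, stopping is a change in A(k), which the printed formula covers, and Section 8.2 conflicts with it. Disenrollment would still need a correct censoring weight.

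**The case against.** The strongest reply is that the wording is shorthand for each patient's observed status. The numerator sentence refers to observed treatment, and for retained person-time the observed censoring status is uncensored, which gives the right weight. The same shorthand has to be allowed for treatment. Taken literally, one over the probability of receiving treatment would also be wrong for untreated periods, yet the printed density of A(k) plainly means observed treatment. The promise of censoring weights also means that their absence from the formula does not prove that none will be applied. This stands: a reader might infer that censoring must be either uncorrected or corrected backwards, and the documents do not support so exhaustive a choice.

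A reader might also infer that every hazard ratio and cost ratio in objectives 2-5 will be biased in favour of anticoagulation. That is not supported either. The documents give no stopping pattern, and step 5 shows that the sign can reverse. Table 2 dates discontinuation 30 days after run-out, so some early events after stopping stay in treated time.

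Other points limit the consequences without removing the defect. Section 8.7 provides for review and possible truncation of extreme stabilized weights and for balance checks. These may expose a bad weight and would moderate values such as 0.004, but they do not turn the weight the right way round. Objectives 2-5 are secondary and optional, and Section 8.10 disclaims causal conclusions. If those objectives are run, however, their models use these weights.

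**Conclusion.** The point holds as a specification error. The definition and the formula are each faulty for censoring and do not agree with each other. The definition read literally gives an inverted censoring weight, the formula gives none, and only a charitable reading of the word observed gives the correct one. A programmer working from this text could implement any of the three.

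The inversion under the literal definition follows wherever censoring depends on the covariates and needs no other assumption. The percentages above rest on an invented single-covariate set-up, which takes the censoring part separately although the text merges it with treatment. They show that the choice of reading can matter and do not predict this study's results. The size and direction of bias in this study cannot be determined from the documents. The text should be corrected before the weighted analyses are run.

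**What to change.** 1. Delete the reference to being censored from the definition of the propensity score, and bring the weight, numerator and denominator sentences into line.
2. Keep the printed SW as the treatment weight. If treatment is modelled only up to initiation, set the per-period factor to 1 afterwards and carry the cumulative product forward. Setting the whole weight to 1 would discard the confounding adjustment in treated time.
3. Print a separate censoring weight: SWc(t) = product over k of P[C(k)=0 | C(k-1)=0, treatment history, V] / P[C(k)=0 | C(k-1)=0, treatment history, L(k)].
4. Define the final weight as SW x SWc.
5. State which events count as censoring, and reconcile Section 8.2 with the Abstract and the time-varying Cox text on time after discontinuation.

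The cost is wording, one formula, one more pooled logistic model and somewhat more variable weights. No new data are needed.
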